 **GALDERMA** | Title: **43CH1508 Clinical Study Protocol** | Doc id: **MA-29708**

2017-07-05 06:37

Effective date:

Effective

Version: 5.0

Storage

Store up to 25° C. Protect from freezing and sunlight.

Date of manufacture

The date of manufacture is indicated on package.

Shelf life

The shelf life of the product is 36 months from the date of manufacture. The expiry date is indicated on package.

Manufacturer/Applicant

Name: Q-Med AB
Registration address: [name]
Manufacturing address: [name]
[name]
[contact]
[contact]

Legal Agent/After Sales Service Agent

Name: Q-Med International Trading (Shanghai) Co., Ltd.
Address: [name],
China
[contact]
[contact]

Others

For more information about the product, please consult Q-Med International Trading (Shanghai) Co., Ltd., the after sales service agent of the Swedish company Q-Med AB, or visit the website below:

www.restylane.com.cn

[figure not shown]
Restylane, 瑞藍, NASHA and Galderma are trademarks owned by Nestlé Skin Health S.A.

Note! The product 瑞蓝 2 (Restylane) to be sold in China must be specially packed by the Swedish company Q-Med AB according to the requirement of China Food and Drug Administration, P.R.China. 瑞蓝 2 (Restylane) must only be purchased through the sales channels of the Swedish company Q-Med AB.

Assembly of Needle to Syringe

For safe use of 瑞蓝 2 (Restylane) it is important that the needle is properly assembled to the syringe. Improper assembly may result in separation of the needle and syringe during injection.

Hold firmly around the syringe barrel with the thumb and forefinger. Grasp the needle shield with the other hand. To facilitate proper fastening, both **push and rotate** them firmly together. See picture. Strict aseptic technique must be followed.

Effective date: 2017-07-05 06:37

Effective date:

Symbols on Package

Lot Number

Use by

Sterile. The contents of the syringe have been sterilized by using moist heat.

Date of manufacture

Do not re-use

Sterile. The needles have been sterilized by using irradiation.

First issue date: *March 2009*Revision date: *September 2016*

Version: 5.0

 GALDERMA	<small>Title</small> 43CH1508 Clinical Study Protocol	<small>Doc id</small> MA-29708
---	---	--

2017-07-05 06:37

Effective date:

Effective

Version: 5.0

1.1.1 Study design

This is a randomized, evaluator-blinded study to evaluate the efficacy and safety of Restylane Defyne (with lidocaine) compared to Restylane (without lidocaine) for correction of moderate to severe nasolabial folds (NLFs) in subjects of Chinese origin, men or women aged 18 years or older.

The study will be conducted at 4 sites located in China, and subjects with a Wrinkle Severity Rating Scale (WSRS) score of either 3 or 4 on both sides, as assessed by the Blinded Evaluator, will be enrolled. The subjects will be followed for up to 14.5 months.

Blinding will be accomplished by a Blinded Evaluator, to whom randomization and treatment are concealed, to evaluate the WSRS score. The treating Investigator will not be blinded. To minimize inter-observer variability, a subject should preferably be assessed by the same individual at the initial Baseline determinations and all follow-up evaluations.

For more details regarding the study, and references, please see the Clinical Study Protocol (CSP), MA-29708.

1.1.2 Number of subjects and randomization

Approximately 175 subjects will be enrolled and treated with Restylane Defyne in one NLF and Restylane in the opposite NLF, as randomly assigned to one of the two possible treatment sequences:

[figure not shown]
- Restylane Defyne in the subject's right NLF followed by Restylane in the subject's left NLF, or
- Restylane in the subject's right NLF followed by Restylane Defyne in the subject's left NLF.

1.2 Study Objectives

1.2.1 Primary Objective

The primary objective is to evaluate the efficacy of Restylane Defyne compared to Restylane in correction of NLFs by comparing the response rates based on the WSRS score, as assessed by the Blinded Evaluator at 6 months after last treatment.

 GALDERMA	<small>Title</small> SAP, 43CH1508, Restylane Defyne NLF	<small>Doc id</small> MA-31549
--	--	--

1.2.3 Safety objectives

The safety objectives are:

- To evaluate the safety of Restylane Defyne and Restylane during the whole study by collecting adverse events (AEs).

1.3 Efficacy Assessments

1.3.1 Wrinkle Severity Rating Scale (WSRS)

WSRS is a 5-grade validated photograph-based scale designed for quantifying facial folds. Scoring of fold severity is based on a visual assessment of the length and depth of the NLF at a certain time point, not in comparison to the Baseline or pre-treatment appearance, see Table 1-1. Each score in the WSRS is exemplified by a photograph of NLFs.

 GALDERMA	Title SAP, 43CH1508, Restylane Defyne NLF	Doc id MA-31549
---	--	--------------------

Table 1-1: Wrinkle Severity Rating Scale (WSRS)

Grade	Description
1	Absent: No visible fold; continuous skin line.
2	Mild: Shallow but visible fold with a slight indentation; minor facial feature. Implant is expected to produce a slight improvement in appearance.
3	Moderate: Moderately deep fold; clear facial feature visible at normal appearance but not when stretched. Excellent correction is expected from injectable implant.
4	Severe: Very long and deep fold; prominent facial feature; less than 2 mm visible fold when stretched. Significant improvement is expected from injectable implant.
5	Extreme: Extremely deep and long fold; detrimental to facial appearance; 2 to 4 mm V-shaped fold when stretched. Unlikely to have satisfactory correction with injectable implant alone.

The Blinded Evaluator will perform assessment of each NLF using the WSRS at Screening, Baseline, and each follow-up visit.

CCI

 GALDERMA	Title SAP, 43CH1508, Restylane Defyne NLF	Doc id MA-31549
--	--	----------------------------------

1.3.4 Photography

Digital photographs, taken of each subject pre-treatment at visits when treatment is performed,

CCI

1.4 Efficacy Endpoints

1.4.1 Primary efficacy endpoint

The primary efficacy endpoint is the response rate based on the WSRS score, as assessed by the Blinded Evaluator at 6 months after last treatment.

Response rate is defined as the percentage of subjects with at least one (≥ 1) grade improvement on the WSRS.

 GALDERMA	Title SAP, 43CH1508, Restylane Defyne NLF	Doc id MA-31549
---	--	--------------------

Effective date:

2017-02-13 08:27

Effective

CCI

1.5 Safety Assessments

The methods for collecting the safety data are described in Section 8 of the CSP and include assessments of CCI laboratory assessments, ECG-screening, adverse events (AEs), serious adverse events (SAEs), and device deficiency.

CCI

A two-point scale ('Yes' or 'No') will be used to assess causality of AEs, serious as well as non-serious. The investigator shall be asked to indicate a response to each of the following questions in the electronic case report form (eCRF):

- *"Do you consider that there is a reasonable possibility that the event may have been caused by the study product?"* and
- *"Do you consider that there is a reasonable possibility that the event may have been caused by the study product injection procedure?"*

If any of these questions are answered with a 'Yes', the AE will be considered related.

Version: 1.0

 GALDERMA	Title SAP, 43CH1508, Restylane Defyne NLF	Doc id MA-31549
--	--	----------------------------------

Each AE will also be assessed for causal relationship and seriousness by the Sponsor, in order to fulfill regulatory requirements. In case of a disagreement, the AE will be considered '*Related*'.

Digital photographs, taken at all follow-up visits, will be used to document AEs in the treated area. If necessary, the photo should be taken when AEs occur. Note that no covering make-up should be used on the photographs.

Any device deficiencies discovered in relation to treatment at Baseline and Week 4 follow-up visits will be recorded.

1.6 Safety Endpoints

Safety endpoints include:

- (i) **Incidence, intensity, duration and time to onset of related treatment emergent AEs collected during the whole study**

CCI

2 Statistical Methods

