4.4.2 Blinding

Due to the differences in the physical characteristics (viscosity) of the study products and the difference in syringe design and material (size of syringe and plastic *vs* glass syringe), it is not possible to truly double-blind the study, and the treatment assignment cannot be obscured from the treating Investigator.

Because the method of administration is similar, the treatment can be masked from the subjects by simply preventing them from viewing the syringes during administration of the study products. This will be done by placing an opaque drape or patch over the subject's eyes during the injection procedure.

The blinded evaluator shall not be allowed to retrieve study supplies or to be present during opening of the study supplies or injections. The treating Investigator is not allowed to discuss treatments with the blinded evaluator or the subjects. All documents with information on study products shall be kept in a separate binder not available to the blinded evaluator. The blinded evaluator should not have access to eCRF pages with study product information.

The Sponsor and the Sponsor's representative at the site shall not be blinded during the study.

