8.4.3.2 Causal relationship and seriousness

Each AE, serious as well as non-serious, shall be assessed by the treating Investigator for causal relationship with the study product and its use (the injection procedure) and for seriousness (Yes or No) of the event.

A two-point scale (Yes or No response) shall be used for the causality assessments. The Investigators shall be asked to indicate a response to each of the following questions in the eCRF:

- “Do you consider that there is a reasonable possibility that the event may have been caused by the study product?”, and
- “Do you consider that there is a reasonable possibility that the event may have been caused by the study product injection procedure?”

If any of these questions is answered Yes, the AE is considered related.

Each AE will also be assessed for causal relationship and seriousness by the Sponsor, in order to fulfil regulatory requirements.

 GALDERMA	Title 43CH1508 Clinical Study Protocol	Doc id MA-29708
--	---	----------------------------------

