2.2 Analysis Populations

The following populations will be defined:

- Full Analysis Set (FAS) Includes all subjects who were injected in both NLFs. Subjects are analyzed according to the randomization assignment.
- Per protocol (PP) Includes all FAS subjects who completed the Month 6 follow-up visit without any major deviations.
- Safety Includes all subjects who were injected in at least one NLF, based on the as treated principle.

The FAS population is the primary population for all efficacy analyses. If there are any CSP deviations considered to have substantial impact on the efficacy outcome at the Month 6 follow-up visit, a PP population excluding those subjects will be defined. As this is a non-inferiority trial, non-inferiority will need to be shown in both FAS and PP analyses. Safety analysis will be performed based on the Safety population set.

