2.5 Safety Analysis

All safety variables will be summarized descriptively based on the safety population.

CCI

2.5.2 *Adverse events*

All AEs will be coded according to MedDRA. Treatment emergent adverse events (TEAEs) will be summarized by System Organ Class (SOC) and Preferred Term (PT). The same summaries will be generated for treatment emergent related AEs, severe AEs, AEs leading to discontinuation, and serious AEs (SAEs). An overall summary of number and percentage of subjects with TEAEs reported in total, no TEAEs reported, related and unrelated TEAEs, and the number of events will be compiled (Table 9-5).

For related TEAEs, intensity of the AE will be summarized (Table 9-6). The number of days to onset (Table 9-8) and duration of event (Table 9-7) will be summarized by SOC and PT using number of events, mean, standard deviation, minimum, median, and maximum statistics. Action taken due to a related TEAE will be summarized by SOC, PT, and treatment (Table 9-9) using number of events.

Number and percentage of subjects with unrelated TEAEs and number of events will be presented by SOC, PT and intensity (Table 9-10).

Time to onset of a TEAE will be derived as the start date minus Day 1. If the start date is missing, it will be assumed that the AE started on Day 1.

Duration of a TEAE will be derived as the stop date minus the start date +1. If the start date is missing, it will be assumed that the AE started on Day 1. Missing stop date will not be imputed and therefore no duration will be calculated in these cases. Instead, the number of TEAEs that were ongoing at the end of the study will be given.

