9.3 Adverse Events

9.3.1 *Summary of treatment emergent Adverse Events (TEAEs)*

Table 9-5: Brief summary of all TEAEs, Safety population

	Events	Subjects	
		n	%
Any AEs reported, total			
of which were serious			
AEs related to product and/or injection procedure			
of which were serious			
Restylane Defyne			
Restylane			
AEs unrelated to product and/or injection procedure			
of which were serious			
No AEs reported			

% = n / number of subjects in Safety population (N = xxx) * 100

 GALDERMA	Title SAP, 43CH1508, Restylane Defyne NLF	Doc id MA-31549
--	--	--------------------

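### In the visible adverse event tables, products are compared only on events judged related by unblinded assessors, and the product percentages use a denominator that can include subjects not given that product

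*SAP*

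**What the plan says.** The safety objective (SAP 1.2.3, Protocol 3.1.3) is to evaluate both products by collecting adverse events, with no causality filter. The visible endpoint in SAP 1.6 is narrower: "Incidence, intensity, duration and time to onset of related treatment emergent AEs collected during the whole study".

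The table shells follow the endpoint. In Table 9-5 the two product rows stand under the related events only; the total and unrelated rows have no product split. Tables 9-6 to 9-9 are split by product and cover related events only. For the rest, SAP 2.5.2 says: "Number and percentage of subjects with unrelated TEAEs and number of events will be presented by SOC, PT and intensity". Treatment is not named there, although the same section names it for action taken on related events.

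On who decides, Protocol 8.4.3.2 says that each event "shall be assessed by the treating Investigator for causal relationship with the study product and its use". SAP 1.5 adds an assessment by the Sponsor. Protocol 4.1 and 4.4.2 leave the treating Investigator unblinded, and 4.4.2 adds that the Sponsor and its "representative at the site shall not be blinded during the study". The rule for relatedness covers two questions, one on the product and one on the injection procedure: "If any of these questions are answered with a 'Yes', the AE will be considered related". A disagreement between Investigator and Sponsor also counts as related.

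On the denominator, the footnote to Tables 9-5 and 9-6 defines the percentage as "n / number of subjects in Safety population (N = xxx) * 100". SAP 2.2 defines that population thus: "Includes all subjects who were injected in at least one NLF, based on the as treated principle". The FAS, by contrast, requires injection in both folds.

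**The concern.** In a split-face trial, the side of a localised event identifies the product through the treatment record. A product comparison of fold-located events therefore needs no opinion on cause. The visible tables make such an opinion the condition of entry, and both people who give it know which product is in which fold. If they were readier to call an event related on one side than on the other, the table would show a product difference that is not in the events themselves, or hide one that is.

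The denominator raises a separate point. A subject injected in one fold only, or given the same product in both folds (a deviation foreseen in SAP Table 2-1), would count in the denominator of a product never received. That lowers the rate shown for that product and sits badly with the as-treated principle.

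**Working it through.** The documents give no numerical safety figure, so there is nothing to reproduce. Safety is descriptive (SAP 2.5), so no significance level, power or margin is involved.

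**Can an event leave the comparison?** Yes, if the Investigator answers No to both questions and the Sponsor also judges it unrelated. It is then counted among the unrelated events, for which no product split is stated.

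**What would differential judgement do?** Let p be the true incidence of fold-located events, equal for both products, and s the probability that an event is called related, with one event per affected subject and side. The table shows p × s, so the spurious difference is p × (s1 − s2). All values of p and s below are assumptions.

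| p | s1, s2 | Shown | Spurious difference |
|---|---|---|---|
| 20% | 0.90, 0.80 | 18.0% v 16.0% | 2.0 points |
| 10% | 0.95, 0.80 | 9.5% v 8.0% | 1.5 points |
| 30% | 0.95, 0.90 | 28.5% v 27.0% | 1.5 points |
| 30% | 0.95, 0.80 | 28.5% v 24.0% | 4.5 points |
| 50% | 0.95, 0.80 | 47.5% v 40.0% | 7.5 points |

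With s1 = s2 the difference is zero, and exchanging the two reverses its sign. With about 175 subjects (SAP 1.1.2), each subject whose only fold event is called unrelated moves that product's incidence by 1/175 = 0.57 points.

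**What does the denominator do?** Let N = 175, and let k be the number of Safety subjects who did not receive a given product. The rate shown is p × (N − k)/N, so the understatement is p × k/N. Again p and k are assumptions.

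| p | k = 0 | k = 1 | k = 2 | k = 5 |
|---|---|---|---|---|
| 10% | 0 | 0.06 | 0.11 | 0.29 |
| 20% | 0 | 0.11 | 0.23 | 0.57 |
| 50% | 0 | 0.29 | 0.57 | 1.43 |
| 80% | 0 | 0.46 | 0.91 | 2.29 |

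Entries are percentage points if all k subjects miss the same product. If they are split evenly, each product loses half as much and, at equal incidence, the difference between products is unaffected. Treatment always starts in the right fold, with the product there randomised (Protocol 4.4.1). Stopping after one injection should therefore affect both products about equally, unless the product itself causes the stop. Tables 9-7 to 9-9 show no percentages of subjects, so this point touches Tables 9-5 and 9-6 only.

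**Can side be recovered?** Usually, it seems. Protocol 8.4.3 has the affected area recorded where applicable, and the treatment record links side to product. Protocol 2.4.2 reports that most product-related events in the earlier US split-face study were associated with a treatment side. However, no explicit left/right field is stated.

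**The case against.** The best defence is that the route out of the comparison is narrow. One Yes, on product or on procedure, makes an event related, and so does a disagreement. The procedure question applies to both folds alike, so most local reactions should be captured. Events called unrelated are still reported, and events not located in a fold cannot be assigned to a product in this design anyway. This stands, and it limits the likely size. It does not remove knowledge of the product from the decision.

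A reader might infer that the plan has no other comparison of adverse events by product. The documents do not support that. Table 7-12 shows directly observed, injection-associated events by treatment, though only in the FAS and only for that class of event. SAP 2.5.2 also promises summaries of all treatment-emergent, severe and serious events and of those leading to discontinuation; it names no product split for them, and no layout is visible. Further safety endpoints and tables are redacted, and the shell of Table 9-10 is not available.

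A reader might also infer that the Safety population does contain subjects given one product. The definition only admits them. Both folds are treated at one visit, so few are likely.

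**Conclusion.** The point holds for the visible adverse event tables. Entry to the product comparison depends on a causality judgement by two unblinded assessors, although a comparison free of that judgement is probably available from recorded location. The size cannot be known from the documents: the spurious differences of 1.5 to 7.5 points come from assumed attribution rates and are not evidence that bias will occur. It would be too strong to say that the safety comparison is biased, or that the whole plan rests on opinion.

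The denominator is wrong in principle whenever a subject receives only one product, but the effect is small: at an assumed 20% incidence, 0.11 points for one subject, 0.57 points for five and zero for none, and probably balanced between products. No formal test is affected. The case for acting rests on the low cost and on matching the tables to a safety objective that is not limited to related events.

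**What to change.** Add to SAP 2.5.2 one descriptive table of all treatment-emergent events located in a treated fold, by the product actually injected in that fold and regardless of causality. Use the recorded affected area where it identifies the side, and show related events as a subset. Keep the planned related-event tables. In the product rows and columns of Tables 9-5 and 9-6, divide by the number of subjects injected with that product; the overall rows and columns can keep the Safety population.

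The cost is one table and a changed footnote, documented in the Clinical Study Report as SAP 2.1 requires for changes to the finalised plan. Events without a recorded side must be shown as not assignable. The new table removes the causality judgement but not every influence of unblinded staff, who also take part in recording events, and should not be described as unbiased.

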2.1 General Methods

All statistical analyses, including summary tables and data listings, will be performed using the SAS® system (version 9). Confidence intervals will be two-sided and constructed at the 95% confidence level.

Continuous endpoints will be summarized using descriptive statistics, e.g., mean, median, standard deviation, minimum, and maximum values. Categorical endpoints will be presented in frequency tables with number and percentage of observations for each level.

Table/graph shells of data summaries are provided in Appendix A-F and are referenced to in the text. All graphs are only examples and will be updated in the Statistical Analysis Report (SAR) to reflect the study data. Any change made to the finalized Statistical Analysis Plan (SAP) will be documented in the Clinical Study Report (CSR).

 GALDERMA	Title SAP, 43CH1508, Restylane Defyne NLF	Doc id MA-31549
---	--	--------------------

2.2 Analysis Populations

The following populations will be defined:

- Full Analysis Set (FAS) Includes all subjects who were injected in both NLFs. Subjects are analyzed according to the randomization assignment.
- Per protocol (PP) Includes all FAS subjects who completed the Month 6 follow-up visit without any major deviations.
- Safety Includes all subjects who were injected in at least one NLF, based on the as treated principle.

The FAS population is the primary population for all efficacy analyses. If there are any CSP deviations considered to have substantial impact on the efficacy outcome at the Month 6 follow-up visit, a PP population excluding those subjects will be defined. As this is a non-inferiority trial, non-inferiority will need to be shown in both FAS and PP analyses. Safety analysis will be performed based on the Safety population set.

